- 5. Co-administration of drugs that compete with memantine for renal elimination using the same renal cationic system, including hydrochlorothiazide, triamterene, metformin, cimetidine, ranitidine, quinidine, and nicotine
- 6. Initiation of a new psychosocial intervention within 30 days prior to randomization.
- 7. Subjects who are pregnant and/or nursing.
- 8. Subjects with a history of non-febrile seizures without a clear and resolved etiology.
- 9. Subjects with a history of or a current liver or kidney disease.
- 10. Clinically unstable psychiatric conditions or judged to be at serious suicidal risk.
- 11. Subjects who meet on the K-SADS-E for alcohol or drug dependence or abuse. If the subject has a recent history of substance abuse, there will be a two-week washout period before initiating the trial as an added precaution. There are no known safety issues relating to memantine and recent history of substance abuse.
- 12. Serious, stable or unstable systemic illness including hepatic, renal, gastroenterological, respiratory, cardiovascular (including ischemic heart disease), endocrinologic, neurologic, immunologic, or hematologic disease.
- 13. Subjects with severe hepatic impairment (LFTs > 3 times ULN).
- 14. Subjects with genitourinary conditions that raise urine pH (e.g., renal tubular acidosis, severe infection of the urinary tract).
- 15. Known hypersensitivity to memantine.
- 16. Severe allergies or multiple adverse drug reactions.
- 17.A non-responder or history of intolerance to memantine, after treatment at adequate doses as determined by the clinician.
- 18. Investigator and his/her immediate family defined as the investigator's spouse, parent, child, grandparent, or grandchild.

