If both parents of the subject are available, we will ask each parent to independently complete an SRS-2 form. Both forms will be scored, and the form with the higher score will be used to determine subject eligibility in order to reduce the possibility of under-recognition of ASD symptoms.

All participants will be required to give a urine sample to test for certain types of drugs. This includes prescription drugs, illegal drugs (street drugs), and controlled substances (substances that may be habit forming) that may affect behavior and that may be regulated by law. Results of the drug screen will be conveyed to the participant by the study clinician and if the results are positive for drug(s) there will be further discussion with the participant to determine if they are appropriate to participate in the trial.

In addition, female ASD and control subjects of childbearing potential will have a urine pregnancy test. If a participant has a positive urine pregnancy test, she will not be able to take part in the study. The study doctor will inform the participant of any positive test results. The decision whether to inform the subject's parent/guardian of these results will be made by the study doctor based on the participant's age and maturity level.

ASD subjects will also be assessed the Autism Diagnostic Observation Schedule (ADOS)⁶⁸. This assessment is recommended, but due to limited ADOS rater availability, it will only be performed if time and schedule of participant and ADOS rater permit. If

determined clinically necessary by study physician, the Clinical Evaluation of Language Fundamentals-Fourth Edition (CELF-4). ASD subjects will complete physical assessment measures (complete physical examination, tanner staging, vitals, height, ECG, and blood screening tests). If a subject refuses a blood draw during the screening visit due to extreme fear and anxiety, they will not be asked to provide a blood sample at the completion visit. For a complete schedule of assessments, refer to the Table I (page 18). The screening process may take place over multiple days, as necessary.

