Participating children and adolescents with ASD who meet the eligibility criteria will be randomly assigned to either memantine or placebo for the course of the 12-week RCT. Subjects will be assessed weekly during the titration phase (Weeks 1-4) & during the maintenance phase at midpoint (Week 6), Week 9, & at completion (Week 12/early termination). The same caretaker (a parent/guardian most familiar with the subject's day-to-day behavior) will participate in the assessment of behavioral symptoms at all visits of the treatment phases.

Randomization: The MGH Clinical Trials Pharmacy will prepare the blinded

memantine and placebo capsules for the study. ASD subjects will be randomized to either active memantine or placebo in a 1:1 ratio after they have been determined to meet all eligibility criteria. Randomization lists stratified by gender and racial/ethnic minority status (minority vs. Caucasian) will be generated by the statistician & passed to the investigational pharmacy for assignment.

Washout Period: ASD subjects who are currently being treated with prohibited psychotropic medications as listed in the exclusion criteria must discontinue the use of their medication to be eligible for participation in this study. Medication washout is recommended by our clinicians to participants, their parent/guardian, and current providers – this is done based on a case-by-case assessment, considering the duration on drug, the dose, and the adverse effects associated with the treatment and effects of stopping that medication/treatment. Our office does not take over care for the patient, but remains available during this time period. The washout schedule –which will span two weeks or more -- will be discussed with the participant, their parent/guardian, and current providers. Individuals taking a medication that is effectively and safely treating their symptoms will not be taken off of such medication for the purpose of enrolling in this study.

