Safety & Tolerability Outcome Measures: The safety & tolerability of memantine treatment will be monitored by administering a complete physical examination, urine tests & ECG at baseline & endpoint of the trial, and by recording AEs and obtaining vital signs at each in-office study visit.

Concomitant Medications/Treatments: As part of the initial psychiatric evaluation, a detailed history of past and present treatments (pharmacological and non-pharmacological) will be obtained. At each study visit, subjects will be assessed for the use of concomitant medication. Subjects will be allowed to take melatonin (up to 3 mg) or Benadryl (up to 50 mg) at bedtime as needed (pm) for insomnia. Non-pharmacological treatments such as supportive individual, family, or group therapy will be permitted provided they were in place for a substantial period of time (> 1 month) prior to the study participation and remain unchanged during the course of the trial. No new non-pharmacological treatments are to be initiated during the course of the trial.

Drop Criteria: A subject may be withdrawn from the study at any time if any of the following conditions are met:

- Worsening of ASD, ADHD, anxiety, depression, mania, OCD or psychosis, as reflected by respective Clinical Global Improvement score of 6 (Much worse) or 7 (Very Much Worse) for 2 visits in a row.
- Subjects who experience intolerable adverse effects, and/or clinically significant laboratory values inconsistent with continuation in the study as determined by PI.
- Unstable psychiatric condition that clinically requires 1) treatment with prohibited concomitant psychotropic medications or 2) subjects requiring inpatient psychiatric admission.
- Emergent suicidality
- Active substance abuse
- Pregnancy
- Allergic drug reaction
- Non-compliance (less than 70% compliance for 2 visits or longer based on parent report)
- Failure to return medication for 2 consecutive visits
- Failure to keep study appointments for more than 2 consecutive visits without justification
- Clinical judgment of the investigator
- Withdrawal of consent

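### The refusal rule for the screening blood draw implies that a subject can be randomised with no blood result, which conflicts with the LFT-based exclusion and the condition for randomisation

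*Combined protocol and SAP*

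**What the plan says.** Four places in the combined protocol and SAP bear on this.

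- **Section VII, Study Procedures (screening).** ASD subjects complete a set of physical measures: "complete physical examination, tanner staging, vitals, height, ECG, and blood screening tests". The next sentence opens "If a subject refuses a blood draw during the screening visit due to extreme fear and anxiety" and gives one consequence: "they will not be asked to provide a blood sample at the completion visit". It does not mention screen failure, a repeat attempt or a substitute test.
- **Section IV, Exclusion Criteria.** Item 13 excludes "Subjects with severe hepatic impairment (LFTs > 3 times ULN"). Item 9 separately excludes "Subjects with a history of or a current liver or kidney disease", and item 12 excludes serious systemic illness, naming hepatic and renal disease among others.
- **Section VII, Randomization.** ASD subjects are assigned 1:1 "after they have been determined to meet all eligibility criteria".
- **Table I.** The blood draw row has two entries, Screening and Week 12, both for ASD subjects only.

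**The concern.** Item 13 has a numeric laboratory threshold, so it can be judged only with a liver test result in hand. The refusal sentence appears to let a subject pass through screening without one. Followed as written, the plan would let a child start study drug with one exclusion criterion never evaluated, although the Randomization paragraph says that cannot happen.

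This is a matter of patient safety and of clear eligibility. Two clinicians could read the sentence differently, one enrolling the refuser and the other treating the refuser as a screen failure. Both could claim to be following the protocol.

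**Working it through.** The plan gives no figure to reproduce, and no power or error-rate calculation is involved. The check sets the rules side by side and counts the scheduled draws.

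1. **Does the refusal rule imply continued participation?** The 12-Week RCT subsection of Section VII places the completion visit at Week 12 or early termination. Only a subject who has entered the trial phase has such a visit. If refusal meant screen failure, there would be nothing to waive. The sentence therefore has a purpose only if the refuser is randomised and treated.

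2. **Is that reading consistent with how the protocol writes its other rules?** Where a screening finding ends or limits participation, the protocol says so. A positive pregnancy test bars the subject. An ASD subject who refuses the scan loses only the imaging component. The ADOS and CELF-4 are expressly conditional. For blood refusal, the only stated consequence is the waiver of the later sample.

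3. **Can item 13 be determined without blood?** No. It is an LFT value compared with three times the upper limit of normal. Items 9 and 12 can be applied from history and examination, but neither shows whether that threshold is exceeded in a child with no known or apparent liver disease.

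4. **Can the refuser then be randomised under the Randomization paragraph?** Not on its wording. It requires all criteria to have been determined to be met, and item 13 has not been. No exception or missing-result rule appears anywhere.

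5. **Could a result come from elsewhere?** Section V allows reuse of screening data from the general screening protocol within the past 8 weeks. This covers only subjects referred from that protocol, and the text does not say that those data include liver tests. The other reuse provisions in Section VII cover diagnostic and cognitive assessments.

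6. **Count of scheduled blood draws from Table I.**

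| Subject | Screening | Baseline to Week 9 | Week 12 | Total |
|---|---|---|---|---|
| ASD, accepts | 1 | 0 | 1 | 2 |
| ASD, refuses at screening | 0 | 0 | 0 | 0 |

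A refuser therefore has 0 of 2 scheduled samples. The documents give no refusal rate, so the number of subjects affected cannot be computed. The conflict between the rules does not depend on that number.

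**The case against.** The strongest reply is that nothing says outright that a refuser is randomised. On this view the Randomization paragraph governs, and the sentence is merely loose. It is true that continued participation is implied and not stated. But the reply leaves the waiver without a purpose, and the protocol still does not say what happens to item 13.

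Second, there is mitigation. Screening may run over several days, Section III allows up to eight weeks for screening and the baseline scan, and Section VII (Risks and Discomforts) offers a topical anaesthetic. These may make final refusals fewer. They do not settle the status of a subject who does refuse.

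Three stronger readings are tempting, and the documents do not support them:

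- **A reader might infer that refusers have no liver screening.** Items 9 and 12 and the complete physical examination still apply. The gap is the laboratory threshold in a child without known or apparent disease.
- **A reader might infer that the laboratory withdrawal condition fails for refusers in particular.** The Drop Criteria refer to "clinically significant laboratory values inconsistent with continuation in the study as determined by PI". Table I schedules no blood between baseline and Week 9 for anyone, so scheduled blood can hardly trigger withdrawal during treatment in any subject. The criterion is permissive and rests on judgement, and unscheduled draws are not barred. This is not a refuser problem.
- **A reader might infer that the safety comparison is biased, or that each refuser removes a fixed share of an arm's laboratory safety data.** Refusal occurs at screening, before assignment, so it does not by itself favour either arm. The safety measures named in the text include "urine tests & ECG at baseline & endpoint of the trial" and do not mention blood. Refusers still contribute urine tests, ECG, adverse events and vital signs.

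**Conclusion.** The point holds as a conflict between stated rules. The refusal sentence implies randomisation and treatment with no blood result, while item 13 and the Randomization paragraph together require one. For each refuser, one laboratory-defined exclusion goes unevaluated and 0 of 2 scheduled blood samples are obtained.

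This rests on two readings. The first is that the completion-visit waiver presupposes participation, which is the natural sense but is not explicit. The second is that the screening blood tests are the intended source of the liver result; the tests in that panel are not listed. The number of refusers is unknown. The point should be corrected because it concerns children receiving study drug and costs little to settle. It does not extend to the laboratory withdrawal condition or to bias between the arms.

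**What to change.** Reconcile three places: exclusion item 13 in Section IV, the blood-refusal sentence in the screening part of Section VII, and the Randomization paragraph in Section VII. The reconciled text should state:

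- whether an ASD subject with no screening blood result may be randomised; and
- if so, how item 13 is determined for that subject, and from what source.

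Which clinical rule to adopt is for the sponsor and investigators.

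The cost is a short protocol amendment. Depending on the rule chosen, a few subjects may become ineligible. No change to the sample size or the analysis follows from this point.

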Dose Titration Phase (Weeks 1-4): Study medication will be initiated at 2.5 mg/day, will be raised to 5 mg/day on day 4, and will be gradually up-titrated by 5 mg/week to a maximum dose of 20 mg/day. Titration of the study medication will be guided by the (following) forced titration schedule with an option for slower titration or holding at lower dose per clinician judgment. Memantine will be administered in twice daily divided dosages with a total daily dose of \geq 2.5 mg/day.

Study Medication Dosing: Study medication (memantine/placebo) will be titrated to the maximum daily dose during the first 4 weeks of the trial (dose titration phase). Subjects will follow the following forced titration schedule until Week 4 when subjects will be maintained on maximum achieved dose until the end of the trial (dose maintenance phase; Weeks 5-12). During the dose maintenance phase, there will be a one-time option to decrease the dose of the study medication.

Mema	antine Forced	Titration Schedule
Visit	Day	Maximum Total Dose Prescribed (mg/day)
0	1	2.5
	5	5
1	8	10
2	15	15
3	22	20
4	28	Maintained on maximum achieved dose

Primary Outcome Measure of Efficacy: Clinician-rated CGI-Improvement (CGI-I) subscale and the parent-rated SRS-2. Treatment responders will be defined as those who demonstrated improvement of ≥25% on the SRS-2 total raw score *and* a score of 2 or 1 on the CGI-I subscale ("much" or "very much improved").

Secondary Outcome Measures of Efficacy: As with other psychotropic treatment outcomes in this population⁷², response to memantine may not be uniform for all domains of ASD. The response differential will be examined by assessing change in the severity of the subscales of the SRS-2 representing core domains of ASD, change on the ABC-SW subscale, and change on the MGH-ASD-RS (clinician- and informant-rated). The CY-BOCS-PDD⁷³⁻⁷⁴ will be administered to assess change with treatment in the ritualistic behaviors associated with ASD. Change with treatment in the level of adaptive functioning will be assessed by the CBCL. Change in the level of global functioning will be assessed by the parent/guardian-rated SAICA. Considering that features of ADHD, anxiety, & depression are frequently associated with ASD⁴ & there is evidence of memantine's effectiveness in treating ADHD in adults, these symptoms will be assessed by administering the clinician-rated ADHD-SCL, CDRS-R⁷⁹, & CASI-Anx⁸⁰.

Safety & Tolerability Outcome Measures: The safety & tolerability of memantine treatment will be monitored by administering a complete physical examination, urine tests & ECG at baseline & endpoint of the trial, and by recording AEs and obtaining vital signs at each in-office study visit.

Concomitant Medications/Treatments: As part of the initial psychiatric evaluation, a detailed history of past and present treatments (pharmacological and non-pharmacological) will be obtained. At each study visit, subjects will be assessed for the use of concomitant medication. Subjects will be allowed to take melatonin (up to 3 mg) or Benadryl (up to 50 mg) at bedtime as needed (pm) for insomnia. Non-pharmacological treatments such as supportive individual, family, or group therapy will be permitted provided they were in place for a substantial period of time (> 1 month) prior to the study participation and remain unchanged during the course of the trial. No new non-pharmacological treatments are to be initiated during the course of the trial.

Drop Criteria: A subject may be withdrawn from the study at any time if any of the following conditions are met:

- Worsening of ASD, ADHD, anxiety, depression, mania, OCD or psychosis, as reflected by respective Clinical Global Improvement score of 6 (Much worse) or 7 (Very Much Worse) for 2 visits in a row.
- Subjects who experience intolerable adverse effects, and/or clinically significant laboratory values inconsistent with continuation in the study as determined by PI.
- Unstable psychiatric condition that clinically requires 1) treatment with prohibited concomitant psychotropic medications or 2) subjects requiring inpatient psychiatric admission.
- Emergent suicidality
- Active substance abuse
- Pregnancy
- Allergic drug reaction
- Non-compliance (less than 70% compliance for 2 visits or longer based on parent report)
- Failure to return medication for 2 consecutive visits
- Failure to keep study appointments for more than 2 consecutive visits without justification
- Clinical judgment of the investigator
- Withdrawal of consent

If study participation is discontinued due to safety reasons, participants will receive three follow-up visits, giving adequate time for appropriate psychiatric referrals to treaters in their community. If emergent suicidality were to occur during the course of the study, the supervising clinician will then directly assess the level of risk and take the appropriate action (including contacting treatment providers, working on a safety plan, arranging for emergency evaluation via an ER, calling 911, etc.) The clinician will document the actions taken, and it will be noted in the participant's file. Subjects who discontinue due to non-compliance with the protocol will receive a referral to ASD treaters in the area.

¹HMRS Scanning (ASD and Healthy Control Subjects):

All subjects eligible for scanning will complete two scanning sessions at the McLean Imaging Center over the course of the study. For subjects with ASD, the initial scan will take place after evaluation and screening and prior to randomization. ASD participants will have a second scanning session at McLean between the 10th and 12th week of treatment.

Upon signing consent/assent at MGH, healthy control subjects will participate in screening procedures to assess eligibility. Those who meet eligibility criteria and complete screening procedures will participate in two scanning sessions at McLean Imaging Center. The first scanning session will take place after screening procedures are completed at MGH, and the second scanning session will take place approximately 10-12 weeks after the first.

During the first scanning visit, subjects will undergo a urine drug screen to determine recent drug use, and all women of childbearing potential will be asked to undergo a urine pregnancy screen. A breath sample will be obtained to screen for alcohol. These procedures will be repeated when subjects return to complete for their second scanning visit. Additionally, parents/guardians of all eligible subjects will complete the Child Behavior Checklist (CBCL) during the first scanning visit at McLean Imaging Center in order to assess the child's maladaptive emotional and behavioral problems at the time of the scan.

At the first scanning visit, the MR protocol will consist of anatomical, diffusion weighted, resting state fMRI multiband, and spectral data acquisitions. The visit will consist of two separate scans: DTI, anatomical, and multiband resting state fMRI scans (35 minutes) will be performed on the 3 Tesla scanner (Siemens Trio) with a full TIM upgrade in place using a 32-channel phased-array head coil. MRS scans (60 minutes) will be acquired on a 4 Tesla Varian Unity/Inova whole body MR scanner (Varian NMR Instruments, Palo Alto, CA) equipped with proton TEM volumetric head coil (MR Instruments, Minneapolis, MN). At the second scanning visit, the MRS protocol will be repeated on the 4T scanner, and only the multiband resting state protocol will be repeated on the 3T scanner. Anatomical MR images will be used for ruling out clinically significant central nervous system disorders. It will be comprised of an axial highresolution T1-weighted MRI obtained with a magnetization-prepared rapid acquisition of gradient echo sequence (TR/TE=2100/2.74 ms, acquisition time=5 minutes), a double echo T2-weighted conventional spin echo MRI (TR/TE=4000/33 ms, acquisition time=2 minutes), and a fluid-attenuated inversion recovery MR imaging sequence (TR/TE=9820/95 ms, acquisition time=3 minutes). No contrast agent will be injected. A board-certified neuroradiologist will review the anatomical MRIs. Individuals with structural brain abnormalities on MRI will be referred for a neurological evaluation and will not be included in the study.

Diffusion weighted images will be obtained with gradients applied in 72 directions (TE=92 ms, TR=6400 ms, matrix= 128x128, FOV=224x224 mm2, 42 continuous slices of 3.5 mm thickness, b value = 1000 s/mm2, acquisition time = 9 minutes).

Resting-state fMRI multiband EPI data will be obtained with the following parameters: TR/TE = 1500/35 ms, flip angle 66°, matrix = 106×106 on a 212 mm $\times 212$ mm FOV, multiband factor = 6, 72 2.0 mm slices, 520 measurements with acquisition time of 13 min 28 seconds. The total acquisition time on the 3 Tesla scanner will be about 35 minutes.

Proton spectra will be acquired at 4T using a two-dimensional J-resolved (2D-JPRESS) ¹HMRS protocol. A 2D-JPRESS sequence was chosen to improve reliability for spectral fitting of the metabolites, allow analysis of Glu alone versus ratios or combined measures (e.g., Glx), and confirm that measured metabolic differences truly arise from differences in metabolic levels and not from T2 relaxation time differences. An 8 cc (2 x 2 x 2 cm) single voxel will be placed in the ACC along the midline such that the inferior edge of the voxel is parallel to the descending surface of the corpus callosum, as determined by longitudinal relaxation time (T1) images used also for tissue segmentation. Then, 3.375 cc (1.5 x 1.5 x 1.5 cm) a single voxel will be placed bilaterally the right MTL staying clear of the tip of the temporal bone to avoid shimming problems. Data will be collected in 12 TE-stepped spectra with the echo-time ranging from 30 to 250 ms in 20 ms increments, with TR = 2s, averages = 16 (for ACC) & 32 (for MTL), scan duration= 7 minutes (for ACC) & 13 minutes (for MTL). Spectral analysis will be conducted in a fully automated fashion using the commercially available LC Model package (version 6.2-1F). The total time of the MRS data acquisition will be up to 60 minutes, including a three plane set of fast localizers to ensure optimal patient positioning (12 seconds), T1-weighted sagittal and axial images for segmentation and voxel positioning (6 minutes), and local shimming/pulse optimization (15 minutes).

ASSESSMENTS (see Table I)

Autism Diagnostic Observation Schedule (ADOS)⁶⁷

- The ADOS is a semi-structured assessment of communication, social interaction, and play (or imaginative use of materials) for individuals suspected of having autism or other pervasive developmental disorders.
- Consists of four modules, each of which is appropriate for children and adults of differing developmental and language levels, ranging from nonverbal to verbally fluent.

Kiddie Schedule for Affective Disorders and Schizophrenia-Epidemiologic Version (K-SADS-E)⁷⁰

- This is a widely used, semi structured, diagnostic interview with established psychometric properties. It can be effectively administered by clinicians and/or trained non-clinician interviewers in 45 to 90 minutes, although more complex cases may require additional time.
- For all subjects, psychiatric data will be collected from the subject's parent/guardian.

Clinical Evaluation of Language Fundamentals-Fourth Edition (CELF-4)⁸¹

- The CELF-4 is an individually administered test for determining if an individual (5-21 years old) has a language disorder or delay.
- Assesses four aspects of language (morphology and syntax, semantics, pragmatics, and phonological awareness) and can be administered in 30-60 minutes.

Neuropsychological Battery

- Wechsler Abbreviated Scale of Intelligence—Second Edition (WASI-II) Vocabulary and Matrix Subtests: to calculate verbal, performance, and full-scale IQ (Wechsler, 2011).
- The following subtests from the Wechsler Adult Intelligence Scale (WAIS-IV) for 17 and 18 year olds or the Wechsler Intelligence Scale for Children (WISC-IV) for 11-16 year olds: Digit Span, Arithmetic, and Letter/Number Sequencing to assess working memory and Digit/Symbol Coding and Symbol Search to assess processing speed (Wechsler, 2003; Wechsler 2008).

Demographic Interview

• A brief demographic interview will be conducted with the subject's parent to estimate socioeconomic status, as well as collect information about any educational accommodations and past head injuries and/or trauma.

Diagnostic Analysis of Nonverbal Accuracy Scale (DANVA 2)84-85

Subjects will be administered 2 tasks of social competence that test the subject's ability to recognize feelings expressed through faces and paralanguage by children: 1) Child (or Adult) Faces 2) Child (or Adult) Paralanguage. Each computer-administered subtest includes 24 photographs or 24 audio clips of child models (12 female, 12 male per subtest) displaying equal numbers of high- and low-intensity expressions of happiness, sadness, anger, and fear. Both subtests have been standardized and have acceptable internal consistency and reliability⁸²⁻⁸³. This test can be administered for testing social competence in children as young as 3 years of age.

Rating Scales

Parent Rated:

- Social Responsiveness Scale-Second Edition (SRS-2)⁷¹ a 65-item rating scale completed by the parent used to measure the severity of autism spectrum symptoms as they occur in natural settings.
- Behavior Rating Inventory of Executive Function (BRIEF-Parent)⁸⁶ a 78-item rating scale to assess level of executive function deficits.
- Aberrant Behavior Checklist⁶⁹ a 58-item scale completed by the parent and reviewed by a clinician to establish the frequency of problematic or abnormal behaviors
- Child Behavior Checklist (CBCL)⁸⁸ is a parent-report questionnaire that evaluates maladaptive behavioral and emotional problems, both internalizing and externalizing, in children ages 6-18.
- Social Adjustment Inventory for Children and Adolescents (SAICA)⁸⁹ is a semistructured interview administered to the child or parent/guardian that assesses social functioning in children 6-17 years old. Content areas include activities, peer relations, family relations, and academic performance (John et al., 1987).
- MGH- Social Emotional Competence Scale-Informant Rated (MGH-SECS-I): This is a 37-item scale that asks informants to rate subjects on their social competence and abilities on a Likert scale from 0 to 6.

• Pre-MR Checklist: This checklist reviews basic medical history that may be pertinent to MR scanning and potential MR contraindications including metallic implants or claustrophobia.

Clinician Rated:

Clinical Global Impression Scale (CGI)87

 The CGI is a measure of illness severity, improvement, and efficacy of treatment (National Institute of Mental Health, 1985). The score for severity ranges from 1 (normal, not at all ill) to 7 (among the most extremely ill subjects). Improvement ranges from 1 (very much improved) to 7 (very much worse). And lastly, the effectiveness index measures to what extent the subject is experiencing therapeutic effects as well as the level of adverse events they are experiencing. The CGI scale will be used for the assessment of global functioning. Additionally, the following disorder-specific CGIs will also be administered: ASD, ADHD, OCD, psychosis, mania, depression, and anxiety.

Depression

- The Children's Depression Rating Scale (CDRS)⁷⁹ is a widely used observational rating measure of depression severity in children and adolescents.
- CGI-Depression.

Anxiety

- Children and Adolescent Symptom Inventory-5 Anxiety Scale (CASI-Anx)⁸⁰
- CGI-Anxiety.

ADHD

- ADHD Symptom Checklist assesses each of the individual symptoms of ADHD based on the DSM (0-3 on a scale of severity)
- CGI-ADHD.

Psychosis

• CGI-Psychosis.

Obsessive-Compulsive Disorder (OCD)

- The Children's Yale Brown Obsessive Compulsive Scale for PDD (CY-BOCS-PDD)⁷⁴ will be used to assess obsessive and compulsive symptoms. This is a clinician-rated 10-item scale (total range from 0 to 40), with subtotals for obsessions (items 1-5) and compulsions (items 6-10).
- CGI-OCD.

Autism Spectrum Disorder (ASD)

CGI- ASD

- CGI- ASD- Social Interaction.
- CGI- ASD– Mannerisms.
- CGI- ASD– Social Communication.
- MGH ASD Symptom Checklist (MGH-ASD-SCL): The spectrum of ASD symptoms will be screened by using clinician administered MGH-ASD-SCL. This screening instrument adopted items from DSM-5 diagnostic criteria for ASD and assesses for the individual core domains and associated features of ASD.
- Social Emotional Competence Scale–Clinician Rated (MGH-SEC-S-C): This is a 37item scale that assesses social competence and abilities in relation to ASD on a Likert scale from 0 to 8.

Level of Functioning

• DSM Global Assessment of Functioning Scale (GAF)⁷⁶: a composite rating of an individual's overall level of functioning (1= worst to 100 = best).

Safety

- Adverse Experiences: to record any adverse health events experienced during the study, along with duration, severity, cause, treatment, and outcome.
- Concomitant Medications: to record additional medications taken during the study.

VI. BIOSTATISTICAL ANALYSIS

Clinical Data Analysis

Because this is a RCT following subjects over a short period of time, missing data are not expected to impact our analyses such that standard statistical tests will be employed. Changes in the primary outcome measures of efficacy (CGI-I & SRS-2) within & between study groups over time will be tested with longitudinal generalized estimating equation (GEE) regression models (RM) estimated using STATA 12.0 within the framework of the general linear model (GLM). For binary outcomes, logistic RMs will be fit with the binomial family & the logit link. For count data, Poisson RMs will be fit with the Poission family & the log link, for normally distributed data, linear RMs will be fit with the Gaussian distribution & identity link. Each model will predict outcome scores from treatment group (memantine vs. PBO), study visit (ordinal predictor), & the group by visit interaction, which is our test of efficacy. Secondary outcome measures (ABC-SW, GAF, ADHD-SCL, CY-BOCS-PDD, CDRS-R, CASI-Anx, & SAICA) will be examined using models similar to the primary outcome measures. Changes in the tolerability outcome measurements will be tested using Chi-squared tests. All analyses will be intention to treat (ITT).

Neuroimaging Data Analysis

After the 2D-JPRESS dataset is resolved into a series of one-dimensional spectra where each spectrum is modeled and fitted with GAMMA simulated J-resolved basis sets, Glu levels will be derived from the total integral across the J-series. Glu transverse relaxation time (T2) will be obtained from the raw peak vs. TE decay curve fitted with

Levenberg-Marquardt algorithm using an exponential decay function (for Glu T2) convoluted with a polynomial function (for Glu J-coupling) that will be obtained from the GAMMA simulation run with previously measured spectral parameters. Data quality will be assessed by LCModel calculated Full Width Half Maximum (FWHM), Signal to Noise Ratio (SNR) and Cramer-Rao Lower Bounds (CRLB).

The following brain measures will be examined between groups and withinsubject across time (e.g., pre- versus post-treatment and correlations between the measures of brain activity and clinical features):

1) ¹HMRS measures of brain Glu in:

a) ACC

b) MTL

2) measures of resting state functional connectivity of:

- a) dorsal & ventral ACC with prefrontal cortex including VMPFC;
- b) bilateral amygdala with insula & VMPFC;

c) bilateral hippocampus with posterior cingulate cortex.

Pretest-posttest brain activity differences will be analyzed using linear regression models, where treatment group is the primary predictor and pretest measures of brain activity are covariates. A general linear regression model will evaluate the difference between the treatment groups in posttest brain measures while controlling for each subject's pretest measures of brain activity. This approach is equivalent to analyses of covariance (ANCOVA). We will also test if changes in Glu in memantine and placebo (PBO) responders differ from changes in Glu over time in healthy controls (HCs). This requires a three-group comparison: memantine responders vs. PBO responders vs. HCs. We will use a GLM to compare Glu changes from baseline to endpoint. If the direction and magnitude of change among the three groups are the same, there will be no group by time interaction. If the interaction is significant and responders show greater changes compared to HCs, it will indicate that the changes observed in responders are greater than expected from normal changes in Glu activity. We will do follow-up tests to separately test the interactions for each pair of the three groups analyzed.

We also predict normalization of brain activity measures with memantine treatment. "Normalization" will be defined as having achieved a resting state functional connectivity level that is no more extreme than the 95th percentile of the control distribution. Normalization ratings between the memantine and PBO groups will be compared using a logistic RMs. A significant effect would mean an increased likelihood of normalization in memantine-treated subjects.

To test our hypothesis of a significant association between neural and clinical response and between glutamate and functional connectivity response, we will use endpoint clinical efficacy scores as the dependent variable and change in brain activity measures from baseline to endpoint as the independent variables. For our exploratory hypothesis examining neural biomarkers of response to memantine therapy, we will use a GLM with endpoint clinical efficacy scores as the dependent variable, baseline brain activity measures as the independent variables, and baseline clinical scores as a covariate.

Resting state data will be analyzed using a seed driven approach with custom software (Conn)⁸⁸. Data will be slice time corrected, realigned, coregistered, normalized, and spatially smoothed as necessary. Physiological & other spurious sources of noise

will be estimated using the CompCor method, and removed together with movementrelated covariates. The residual BOLD time-series will be band-pass filtered over a lowfrequency window of interest (0.009Hz<f<0.08Hz). Correlation maps will be produced by extracting the residual BOLD time course from bilateral anatomically defined amygdala (WFU_Pickatlas) seed regions, and computing Pearson's correlation coefficients between that time course and the time course of all other voxels. Correlation coefficients will be converted to normally distributed scores using Fisher's transform to allow for second-level General Linear Model analyses. Between group differences will be calculated for each ROI.

Power Considerations

